11.4.1.1 Lesions Too Small to Measure

Lesions that become too small to measure during treatment must be assigned a default measurement of either 0 mm (if the Investigator believes the lesion has disappeared) or 5 mm (if the lesion is still present).

11.4.1.2 Lesions That Split or Coalesce

If a target lesion splits into multiple fragments during treatment, the longest diameters of each fragment should be added together to generate the total sum for that lesion. When lesions coalesce, a plane between them may be maintained that would aid in obtaining maximal diameter measurements for each individual lesion. If the lesions are no longer separable, the vector of the longest diameter in this instance should be the maximal longest diameter for the coalesced lesion.

11.4.2 Nontarget Lesions

All lesions (or sites of disease) not characterized as target lesions (see Section 11.4.1), both measurable and nonmeasurable, will be identified as nontarget lesions and will be recorded at baseline. Measurements will not be required, and these lesions will be followed as “present,” “absent,” or “unequivocal progression” (see below).

Complete Response (CR):

The disappearance of all nontarget lesions, the normalization of the tumor marker level (if tumor markers are measured and are initially above the ULN, those must normalize for a subject to be considered in complete clinical response). All lymph nodes must be <10 mm (short axis).

Non-CR/Non-PD:

The persistence of one or more nontarget lesions and/or the maintenance of the tumor marker level above normal limits.

Progressive Disease (PD):

The appearance of one or more new lesions and/or unequivocal progression of existing nontarget lesions. Progressive disease may be declared on the basis of “unequivocal progression” in cases where the overall tumor burden increases significantly enough to require a change in therapy; in most cases, a modest increase in the size of one or more nontarget lesions is not sufficient to qualify (especially in the presence of stable disease [SD] or PR in target disease).

Inevaluable or Non-evaluable (NE):

A nontarget lesion present at baseline that is subsequently not measured or which is unable to be evaluated or there is a change in the method of measurement from baseline that impacted the ability to make a reliable evaluation of response, leading to an inability to determine the status of that particular tumor for the time point in question. This category also includes scans that are not performed at this time point to evaluate the nontarget lesion(s). The reason(s) explaining the absence of the evaluation or NE nature of the lesion(s) should be specified at the time of the assessment (for example, early death, malignant disease; early death, toxicity; tumor assessments not repeated or incomplete; other [specify]).

11.4.3 New Lesions

The finding of a new lesion should be unequivocal (that is, not attributable to a change in scanning technique or imaging modality, and not thought to represent something other than a tumor). If a possible new lesion is equivocal, treatment and radiological evaluation should continue per this protocol until confirmation of disease progression or until additional scans confirm the presence of a new lesion. In such a case, the date of progression will be the date of the initial scan at which the equivocal new lesion was observed.

A lesion identified on a follow-up study of an anatomical location *not* studied at baseline will qualify as a new lesion.

Fluorodeoxyglucose (FDG)-PET scanning may be employed as a complement to CT scanning in the assessment of possible new lesions. A negative FDG-PET scan at baseline with a positive scan on study will be evidence of PD. If there is no FDG-PET scan at baseline and a positive FDG-PET scan during the study, it will be considered evidence of PD if the positive FDG-PET corresponds to a new site of disease confirmed by CT scan. A positive on-study FDG-PET result corresponding to a preexisting site of disease with no radiological evidence of progression will not be considered evidence of PD.

11.5 Determination of Overall Response

Each response parameter (target, nontarget, and new lesions) will be reported independently at each radiologic read. The Investigator will make a determination of overall response based on the evaluation of target, nontarget, and new lesions, as shown in [Table 13](#).

Table 13. Overall Response

Target Lesions	Nontarget Lesions	New Lesions	Overall Response
CR	CR	No	CR
CR	Non-CR/Non-PD	No	PR
CR	Not Evaluated	No	PR
PR	Non-PD or not all evaluated ^a	No	PR
SD	Non-PD or not all evaluated ^a	No	SD
Not all evaluated ^a	Non-PD	No	NE
PD	Any	Yes or No	PD
Any	PD	Yes or No	PD
Any	Any	Yes	PD

Abbreviations: CR = complete response; NE = non-evaluable or inevaluable; PD = progressive disease; PR = partial response; SD = stable disease.

a In general, if only a subset of lesion measurements are taken at a given assessment time point, the subject as a whole is considered NE for that time point, unless a convincing argument can be made that the contribution of the individual missing lesion(s) would not change the assigned time point response.

For subjects who discontinue therapy for reasons other than disease progression (for example, toxicity), every effort will be made to document tumor measurements and the extent of disease, even after discontinuation of therapy, in order to classify subjects for overall response as described above.

Symptomatic deterioration sufficient to warrant discontinuation of therapy will *not* be considered a descriptor of response, but rather only a reason for stopping therapy. Whenever possible, subjects removed from therapy solely for symptomatic progression should be followed for subsequent radiographic progression. Response evaluation in a subject who discontinues treatment due to symptomatic deterioration in the absence of radiological confirmation of PD should be based on evaluation of target and nontarget lesions as described above.

In some circumstances, it may be difficult to distinguish residual disease from normal tissue. When the evaluation of CR depends upon this determination, it is recommended that the residual lesion be investigated and ruled out (for example, by FNA/biopsy) before confirming the CR status. FDG-PET scanning may also be used to confirm a response of CR under appropriate circumstances (for example, similar to a biopsy in cases where a residual radiographic abnormality is thought to represent fibrosis or scarring).

12 PLANNED STATISTICAL METHODS

12.1 General Considerations

Statistical analysis of this study will be the responsibility of the Sponsor.

The interpretation of the study results will be the responsibility of the investigators with the Lilly CRP or CRS, pharmacokineticist, and statistician. The CRP or CRS and statistician will also be responsible for the appropriate conduct of an internal review for both the final study report and any study-related material to be authorized by Lilly for publication.

The analyses for this study will be descriptive, except for possible exploratory analyses as deemed appropriate. Data analyses will be provided by dose levels and for all subjects combined, wherever appropriate. For continuous variables, summary statistics will include number of subjects (N), mean, median, standard deviation, minimum, and maximum. Categorical endpoints will be summarized using N, frequency, and percentages. Missing data will not be imputed. Exploratory analyses of the data that are not described in the protocol will be conducted as deemed appropriate. A detailed description of data analyses will be provided in a separate statistical analysis plan document for this study.

This is a Phase 1 study with an open-label, dose-escalation design. Subjects will be enrolled into cohorts sequentially without randomization to dose level. During dose escalation, the total sample size per cohort will be guided by the standard oncology 3+3 method and determined by the occurrences of DLTs for the treated subjects. The total sample size for Parts A and B is estimated to be approximately 72 treated subjects. In Part A, the sample size is estimated to be approximately 30 subjects. In Part B, the sample size is estimated to be approximately 9 to 42 subjects.

Pretreatment and posttreatment anti-IMC-CS4 samples will be assayed using an immunoassay. A sample will be considered positive for IMC-CS4 antibodies if it exhibits a postbaseline antibody level that exceeds the upper 95% confidence interval of the mean determined from the normal anti-IMC-CS4 level seen in healthy untreated individuals.

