2.2 Secondary Objectives

The secondary objectives of this study are:

- Part A only – To define the recommended Phase 2 dose (RP2D) using weight-based dosing;
- Part B only – To define the RP2D using non-weight-based dosing;
- To characterize the pharmacodynamic profile of IMC-CS4 on circulating levels of CSF-1; and
- To assess the development of antibodies against IMC-CS4 (immunogenicity).

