6.8 Blood Sampling

Blood will be collected from all subjects for PK, pharmacodynamic, immunogenicity, and other analyses as described in Sections [6.8.1](#), [6.8.2](#), [6.8.3](#), and [6.8.4](#). Samples collected will be retained for a maximum of 15 years (pharmacodynamics, immunogenicity) or 1 year (PK) following the last subject visit for the study, or as previously described in Section [6.5](#).

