6.8.2 Immunogenicity Testing (Anti-IMC-CS4 Antibodies)

Blood samples for the assessment of antibodies against IMC-CS4 (immunogenicity) will be collected for all study subjects at specified time points throughout the study (Section 7.7). In addition, if a subject should have an infusion-related reaction to IMC-CS4, all attempts will be made to obtain a blood sample for immunogenicity analysis as close to the onset of the event as possible, at the resolution of the event, and 30 (calendar) days following the event. For each specified time point, one tube (approximately 7.5 mL/tube) of blood is required; if the timing of a PK sample should coincide with that of an immunogenicity sample, the same sample will suffice for both studies.

In certain circumstances, including if antibodies against IMC-CS4 are detected, the subject's serum IMC-CS4 concentration will be analyzed using the same sample, in order to determine if there is any alteration of IMC-CS4 PK. Detailed instructions for collecting, processing, storing, and shipping of samples will be provided by the Sponsor and its representative(s)/delegate(s) in a separate procedure manual. Refer to Section 7.7 for a detailed schedule of collection time points.

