3.1 Introduction

This statistical analysis plan for protocol CP24-1001 (I5F-IE-JSCA), Version 3.0, dated 28 March 2012, describes the detailed procedures for executing the planned statistical analyses for the clinical study report. Pharmacokinetic, pharmacodynamic and immunogenicity data will be analyzed by the ImClone LLC Clinical Pharmacology department.

The statistical analyses will be conducted by ImClone LLC or a contract research organization (CRO) using SAS® software Version 9.1.3 or higher.

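### Section 12.1 sets antibody positivity at a confidence limit for the healthy mean, so 32% to 44% of antibody-free samples would test positive if levels are near normal and the panel is 20 to 200

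*Protocol*

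**What the plan says.** Protocol Section 12.1 gives the only positivity rule in either document. It counts a sample taken after baseline as positive when the reading "exceeds the upper 95% confidence interval of the mean determined from the normal anti-IMC-CS4 level seen in healthy untreated individuals". One assay is described ("Pretreatment and posttreatment anti-IMC-CS4 samples will be assayed using an immunoassay"), with no confirmatory step. The rule classifies single samples. It does not compare a post-baseline result with the subject's own pretreatment result.

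Section 2.2 makes antibody development a secondary objective. Section 6.8.2 adds a follow-up step for samples in which antibodies are found: "serum IMC-CS4 concentration will be analyzed using the same sample, in order to determine if there is any alteration of IMC-CS4 PK".

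SAP Section 3.1 says only that "Pharmacokinetic, pharmacodynamic and immunogenicity data will be analyzed by the ImClone LLC Clinical Pharmacology department". The SAP lists an antibody table (14.3.26) and a listing (29) but gives no cut point. It announces a separate plan for pharmacodynamics (SAP Section 5.3.5.2) and none for immunogenicity.

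**The concern.** A cut point for classifying individual samples should come from the spread of individual values in people who do not have the antibody. A confidence limit of the mean lies t × SD/√n above the mean, so it shrinks toward the mean as the panel grows. Under normality the false-positive rate then tends to 50%. A larger and better reference panel therefore gives a worse classifier.

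Three things are at stake:

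- The reported incidence for a secondary objective would be inflated.
- Antibody-free samples would be counted as positive in any comparison of drug levels by antibody status, and in reading the antibody samples drawn at infusion-related reactions (Sections 6.8.2 and 9.1.2). Either would dilute a real association.
- A subject already reactive before dosing would have positive post-baseline samples, and nothing says whether that counts as developing antibodies.

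**Working it through.** The protocol states no false-positive rate, so there is no planned figure to reproduce.

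**Inputs.** From Section 12.1: the 95% confidence limit of the healthy mean, applied to one sample. Sidedness is not stated, so two-sided is the main reading. Not in the documents, hence assumed: panel size n, distribution shape, and that antibody-free study samples follow the healthy-panel distribution.

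**Per sample, normal levels.** The cut point is mean + t(0.975, n−1) × SD/√n. The rate for an antibody-free sample is 1 − Φ(t/√n), whatever the mean and SD. Averaging over error in the panel's own mean and SD gives P(T(n−1) > t/√(n+1)).

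| n | Cut point above mean | False positive | Averaged over panel error |
|---|---|---|---|
| 5 | 1.24 SD | 10.7% | 16.0% |
| 10 | 0.72 SD | 23.7% | 25.6% |
| 20 | 0.47 SD | 32.0% | 32.7% |
| 50 | 0.28 SD | 38.8% | 39.0% |
| 200 | 0.14 SD | 44.5% (0.4446) | 44.5% |

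A one-sided 95% limit gives 35.0% at n=20 and 45.4% at n=200.

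**Per sample, right-skewed (lognormal, untransformed, true moments).**

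| n | log-SD 0.5 | log-SD 1.0 |
|---|---|---|
| 20 | 24.3% | 16.4% |
| 50 | 29.7% | 20.7% |
| 200 | 34.7% | 25.2% |

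The lowest case tried is log-SD 1.0 with n=5: 7.1%, or 18.2% when panel error is simulated.

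**Per subject.** In Table 7, a weekly-cohort subject who leaves after Cycle 1 has three post-baseline immunogenicity samples: Day 8, Week 4 and the 30-day visit. With n=50 and normal levels, the chance of at least one false positive depends on the correlation between samples.

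| Correlation | Rule as written | 95th percentile |
|---|---|---|
| 1 | 38.8% | 5.0% |
| 0.8 | 54.0% | 9.2% |
| 0.5 | 63.7% | 11.9% |
| 0 | 1 − 0.612³ = 77.1% | 1 − 0.95³ = 14.3% |

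Independence is an upper bound, because samples from one person will be correlated.

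**Effect on reported incidence.** Example: true incidence 10%, full sensitivity.

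- As written: 0.10 + 0.90 × 0.39 = 45.1%, up to 0.10 + 0.90 × 0.77 = 79.3%.
- 95th percentile: 0.10 + 0.90 × 0.05 = 14.5%, up to 0.10 + 0.90 × 0.143 = 22.9%.

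False positives outnumber true ones when true incidence is below f/(1+f): 0.39/1.39 = 28% at full correlation and 0.77/1.77 = 44% under independence. The true incidence is not given.

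**Replacement rule.** Under normality, mean + 1.645 SD gives 5.0% with a known SD. With mean and SD estimated from the panel it gives 6.2% (n=20), 5.5% (n=50) and 5.1% (n=200), so a larger panel now improves it.

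**The case against.** **The size rests on assumptions.** This is true. Panel size and shape are not in the documents, and the study samples come from treated cancer patients. If most untreated people read at the assay floor and at most 5% read above it, the confidence limit lies above the floor and the false-positive rate cannot exceed 5%. The percentages are therefore conditional. This shape is the exception, though. Every continuous shape tried exceeds 5%, and nothing in the documents points to a floor.

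**The authors may have meant a normal-range limit for individuals.** That is possible, since a value exceeds a limit and not an interval. But the text names the mean, and nothing in either document supports the other reading. If it was the intention, the same correction is needed.

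**The working rule may sit elsewhere.** The SAP supplied was written for protocol Version 3.0 and passes immunogenicity to another department. Neither document refers to a separate immunogenicity rule, so Section 12.1 stands as the rule.

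**The PK consequence is small.** This is largely right. In Table 7 every scheduled immunogenicity time point except Cycle 5 is also a PK time point, so false positives trigger few extra measurements. What remains is dilution of comparisons by antibody status. No formal analysis of infusion reactions by antibody status is planned, but Section 9.1.2 has antibody samples drawn at reactions and allows drug level and pharmacodynamic markers to be assessed to explain them.

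**It is a descriptive secondary objective in a Phase 1 study.** This is also right, and it limits how serious the point is.

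**Conclusion.** The rule is wrong as written. For roughly normal levels, a panel of 20 to 200, and antibody-free study samples that behave like the panel, it calls 32% to 44% of antibody-free samples positive. The lognormal cases give 16% to 35% over the same panel sizes. The defect in the wording is certain; its size depends on a panel and distribution that the documents do not describe. The missing treatment of pretreatment-reactive subjects is a separate, smaller gap. The point should be fixed because a secondary objective would be misreported, but no escalation, DLT or RP2D decision uses antibody status.

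**What to change.** In Section 12.1, replace the confidence limit of the mean with the 95th percentile of individual values from untreated people (mean + 1.645 SD if levels are normal), and state the panel size. Then define antibody development per subject in one of two ways:

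- a post-baseline sample exceeds the cut point and the pretreatment sample did not; or
- the result rises over the pretreatment value by a margin, set from assay variability and given a numerical value before analysis.

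The immunogenicity analysis plan should carry the same rule.

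This is a wording change using the same samples and assay. The sponsor needs the individual healthy-donor values or their SD. Levels already recorded can be reclassified without re-assay. Reported incidence should fall, except possibly where most untreated values sit at the assay floor.

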12.2 Analysis Populations

All enrolled subjects who received at least one dose of IMC-CS4 will be included in the safety population.

Subjects who complete the initial 6 weeks of therapy (that is, receive all scheduled treatments for Cycle 1 and complete the observation period, as needed) or experience a DLT will be included in the DLT population. The DLT population will be used for the determination of the RP2D, including evaluation of DLTs. All other variables (including demographic and baseline subject characteristics, efficacy and safety variables) will be analyzed using the safety population.

12.3 Subject Disposition

All subject discontinuations will be documented, and the extent of each subject's participation in the study will be reported. If known, a reason for discontinuation will be given.

Additional summary of subject participation flow will be performed for the purpose of fulfilling the Clinical Trial Registry (CTR) requirements. A participant flow will describe how many enrolled subjects completed the study, and for those who did not, the frequency of each reason for not completing.

12.4 Demographics and Baseline Characteristics

Baseline demographics, disease characteristics, prior anticancer therapy, and medical history will be listed and/or tabulated by cohort.

12.5 Analyses of Safety Data

12.5.1 Extent of Exposure

Exposure analyses will be based on the actual dose administered (in mg) and body weight (in kg) per the eCRF. The baseline body weight will be used for calculating each dose unless the subject's weight changes $\geq 10\%$ from baseline and a dose change is required. Dose intensity and relative dose intensity will be calculated based on the dose administered and the most recent body weight recorded prior to treatment administration. Exposure analyses will include duration of treatment (weeks), number of subjects treated by cycle, number of infusions per subject,

cumulative dose, dose intensity and relative dose intensity, and number (%) of subjects with dose modifications (reduced or delayed).

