1.5 Human Experience

This is the first study of IMC-CS4 in humans. Limited data are available from this study to date, and are described in Sections 1.4.2 and 1.4.3.

More information about the known and expected benefits, risks, and reasonably anticipated adverse events (AEs) may be found in the IB. Information on AEs expected to be related to the investigational product may be found in Section 7 (Development Core Safety Information) of the IB. Information on serious adverse events (SAEs) expected in the study population independent of drug exposure and that will be assessed by the Sponsor in aggregate, periodically during the course of the study, may be found in Section 6 (Effects in Humans) of the IB.

NOTE:

Protocol Amendment Version 7.0 describes additional cohorts for non-weight-based dosing of IMC-CS4, which will be referred to as Part B of the study. Cohorts described in the protocol prior to Protocol Amendment Version 7.0 (that is, for weight-based dosing of IMC-CS4) will now be referred to as Part A of the study. Refer to Section [4.1](#) for details of the dose assignments for Parts A and B.

Throughout the protocol, information relevant only to Part A (weight-based dosing) or only to Part B (non-weight-based dosing) is indicated as such. Any information not indicated as “Part A only” or “Part B only” is relevant to both parts.

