1	2.5 mg/kg	qw	2 weeks (Weeks 5-6)	Cycle 1: 4 Subsequent cycles: 6
2	0.3 mg/kg	qw	2 weeks (Weeks 5-6)	Cycle 1: 4 Subsequent cycles: 6
3	0.6 mg/kg	qw	2 weeks (Weeks 5-6)	Cycle 1: 4 Subsequent cycles: 6
4	1.25 mg/kg	q2w	3 weeks (Weeks 4-6)	Cycle 1: 2 Subsequent cycles: 3
5	1.25 mg/kg	qw	2 weeks (Weeks 5-6)	Cycle 1: 4 Subsequent cycles: 6
Part B (non-weight-based dosing)				
6a	100 mg	qw	None	Cycle 1: 6 Subsequent cycles: 6
6b ^{c,d}	100 mg	qw on Weeks 1, 2, 4, and 5	None (Weeks 3 and 6 are rest)	Cycle 1: 4 Subsequent cycles: 4
6c ^c	75 mg	qw	None	Cycle 1: 6 Subsequent cycles: 6
7a	150 mg	qw	None	Cycle 1: 6 Subsequent cycles: 6
7b ^{c,d}	150 mg	qw on Weeks 1, 2, 4, and 5	None (Weeks 3 and 6 are rest)	Cycle 1: 4 Subsequent cycles: 4
7c ^c	125 mg	qw	None	Cycle 1: 6 Subsequent cycles: 6
8a	200 mg	qw	None	Cycle 1: 6 Subsequent cycles: 6
8b ^{c,d}	200 mg	qw on Weeks 1, 2, 4, and 5	None (Weeks 3 and 6 are rest)	Cycle 1: 4 Subsequent cycles: 4
8c ^c	175 mg	qw	None	Cycle 1: 6 Subsequent cycles: 6

Abbreviations: aEC = approving Ethics Committee; DLT = dose-limiting toxicity;

IRB = Institutional Review Board; PK = pharmacokinetic(s); qw = weekly; q2w = every 2 weeks.

a – At the highest dose level where major toxicity is observed and that requires a longer recovery period between infusions, a change in the periodicity of dosing (that is, other dosing schedules based on safety and PK considerations) will be agreed upon with the Investigator and communicated to IRBs/aECs.

b – Observation following the fourth infusion in Cohorts 1, 2, 3, and 5 (qw dosing) and the second infusion in Cohort 4 (q2w dosing) in Cycle 1 only. No Cycle 1 observation period for Cohorts 6a, 6c, 7a, 7c, 8a, or 8c. Weeks 3 and 6 of all cycles are rest weeks in Cohorts 6b, 7b, and 8b (qw dosing on Weeks 1, 2, 4, and 5).

c – Concurrently enroll to Cohorts 6b/7b/8b and 6c/7c/8c, should ≥ 2 subjects in Cohort 6a/7a/8a experience DLT events.

d – For all cycles: Infusions on Weeks 1, 2, 4, and 5, and rest on Weeks 3 and 6.

It is recognized that in the course of clinical cancer care, it is not always possible to schedule therapeutic infusions at precise intervals (because of holidays, travel difficulties, or other circumstances). Accordingly, infusions administered within 2 days (all cohorts other than q2w

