5.1.1.2 Part B Only

The dose of IMC-CS4 is non-weight based. Subjects will receive IMC-CS4 I.V. via infusion over a period of 30 minutes. The infusion rate should not exceed 25 mg/minute.

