5.2.1.4 Study Drug Exposure

Exposure analyses will be based on the actual dose administered (in mg) and body weight (in kg) per the eCRF. The baseline body weight will be used for calculating the cumulative dose unless the subject's weight changes $\geq 10\%$. For subjects with a weight change $\geq 10\%$, the revised weight will be used from the time point of the change and onwards.

For analysis of dose exposure **across all cycles** the following definitions will be used:

- **Duration of cycle:**
 - **Patients discontinuing during first cycle:** Duration of cycles (in weeks)² = $(\text{Date of last dose} - \text{date of first dose} + 21) / 7$
 - **Patients discontinuing treatment after start of Cycle 2:** Duration of cycles (in weeks)³ = $(\text{Date of last dose} - \text{date of first dose} + 7) / 7$
- Duration of treatment:
 - **Patients discontinuing during first cycle:** Duration of treatment (in weeks)⁴ = $(\text{Date of last dose} - \text{date of first dose} + 7) / 7$

² 21 days added to duration of cycle because of a 2 week observation period after last dose in cycle 1 (ie, 21 days until the next dose).

³ 7 days added to duration of cycle because administrations are planned every week (starting from Cycle 2).

⁴ 7 days added to duration of treatment because administrations are planned every week. Duration of treatment does not include the 2-week observation period in Cycle 1.

- **Patients discontinuing treatment after start of Cycle 2:** Duration of treatment (in weeks)⁵ = Duration of cycle -14
- Cumulative dose (mg/kg) = Sum of all [administered dosages (mg) / baseline weight⁶ (kg)]
- Dose intensity (mg/kg/week) = Cumulative dose / Duration of treatment
- Planned weekly dose: Refer to Table 1: Planned Dose Regimens
- Relative dose intensity (%) = (Dose intensity / Planned weekly dose) * 100.
- Number of dose reductions: total number of reduction steps comparing the intended dose level before each infusion (as entered in the eCRF) to the protocol planned dose level as referenced in Table 2: General Dose Reduction Guidelines.
- Dose delay within a cycle: a dose is considered delayed if it is administered more than 3 days after the scheduled date relative to the previous administration.

Table 1: Planned Dose Regimens

Cohort	All cycles	Dosing Frequency
1	2.5 mg/kg	Weekly
2	0.3 mg/kg	Weekly
3	0.6 mg/kg	Weekly
4	1.25 mg/kg	Every 2 weeks
5	1.25 mg/kg	Weekly
6	2.5 mg/kg	Every 2 weeks

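### Protocol Section 12.5.1 applies per-kilogram dose intensity to Part B, where doses are fixed in mg, so Part B relative dose intensity is undefined or moves with body weight

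*Protocol*

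**What the plan says.** Protocol Section 12.5.1 sets the basis for all exposure summaries: "Exposure analyses will be based on the actual dose administered (in mg) and body weight (in kg) per the eCRF". It then says that baseline weight is used to calculate each dose unless weight changes by at least 10% and a dose change is needed, and that "Dose intensity and relative dose intensity will be calculated based on the dose administered and the most recent body weight" recorded before treatment. The paragraph ends with the outputs: treatment duration, subjects treated by cycle, infusions per subject, cumulative dose, the two intensity measures, and subjects with reduced or delayed doses.

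Nothing in 12.5.1 limits it to one part. The note in Section 1.5 gives the default: "Any information not indicated as “Part A only” or “Part B only” is relevant to both parts". Section 4.1 repeats it. For Part B, Section 5.1.1.2 says: "The dose of IMC-CS4 is non-weight based".

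The formulas are in SAP Section 5.2.1.4: "Dose intensity (mg/kg/week) = Cumulative dose / Duration of treatment" and "Relative dose intensity (%) = (Dose intensity / Planned weekly dose) * 100". SAP Tables 1 and 2 list Cohorts 1 to 6 only, all in mg/kg. That SAP was written for protocol Version 3.0, before Part B existed.

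**The concern.** A weight-based rule is being applied to doses that do not depend on weight. In Part A, per-kg intensity compares like with like, because the plan is itself in mg/kg. In Part B the plan is a fixed number of mg, so dividing the dose given by current weight adds a quantity unrelated to whether the regimen was delivered. The sentence about calculating each dose from baseline weight also contradicts Section 5.1.1.2 for Part B. The matching weight-recalculation rule in Section 5.1.1.1 is headed as Part A only; 12.5.1 has no such heading.

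At stake is how Part B exposure is described. Establishing the safety profile is a primary objective, and adverse events in a cohort are read against the drug its subjects received.

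**Working it through.** The documents give no relative dose intensity (RDI) figure, so there is nothing to reproduce. The check is direct arithmetic.

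**Inputs**
- Part B doses are 75 to 200 mg (protocol Table 1).
- Weekly cohorts: "Cycle 1: 6 Subsequent cycles: 6" infusions. Cohorts 6b, 7b and 8b have 4 per 6-week cycle.
- Weight is the most recent before each infusion (protocol 12.5.1).
- The RDI formula is that of SAP 5.2.1.4.
- Weight change is an assumption, shown from −15% to +10%, because the documents give none. A 70 kg baseline is used where a weight is needed.

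**1. Units.** At 70 kg, 100 mg weekly is 100/70 = 1.43 mg/kg/week. Protocol Table 1 supplies only mg and a schedule, so the planned figure for Cohort 6a is 100 mg/week. The ratio 1.43/100 mixes units and is not a percentage of plan.

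**2. Dependence on weight.** To obtain a percentage, assume planned mg/kg is the fixed dose over baseline weight. Let n be planned infusions, m those missed mid-course, and r the weight at dosing over baseline weight, held constant:

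per-kg RDI = [(n − m)/n] / r; mg-based RDI = (n − m)/n.

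| Sustained weight change | None missed | 1 of 12 missed | 1 of 6 missed |
|---|---|---|---|
| −15% | 117.6% | 107.8% | 98.0% |
| −10% | 111.1% | 101.9% | 92.6% |
| −5% | 105.3% | 96.5% | 87.7% |
| 0 (equals mg-based) | 100% | 91.7% | 83.3% |
| +5% | 95.2% | 87.3% | 79.4% |
| +10% | 90.9% | 83.3% | 75.8% |

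**3. Offsetting.** A sustained loss equal to the missed fraction cancels it: 0.90/0.90 = 100% for 10% missed. Full cancellation takes a loss of 8.3% for 1 of 12 missed and 16.7% for 1 of 6.

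**4. Gradual change.** For a linear fall from 70 to 63 kg over 12 doses with the sixth missed, per-kg RDI is 96.6% against 91.7% in mg. For a linear rise from 70 to 77 kg with none missed, it is 95.3%. Under the SAP's weight rule (baseline unless the change is at least 10%), the falling case has ten doses at 70 kg and one at 63 kg: (10 + 70/63)/12 = 92.6%.

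**5. When weight drops out.** If planned and given doses are divided by the same constant current weight, it cancels: (5 × 100/63)/(6 × 100/63) = 83.3%. No section specifies this.

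**6. Removing weight is not enough.** Once Cycle 2 has started, the SAP takes 14 days off treatment duration for the Cycle 1 observation period, which Part B lacks (Section 4.1). Twelve full weekly 100 mg infusions span (77 + 7)/7 = 12 weeks, less 2 = 10 weeks. Dose intensity is then 1200/10 = 120 mg/week, or 120% of plan. A Cohort 6b subject stopping after one full cycle has (28 + 7)/7 = 5 weeks and 400/5 = 80 mg/week. The planned average is 100 × 4/6 = 66.7, so this also reads 120%.

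**The case against.** The strongest reply is that little depends on this ratio. The DLT definition (4.1.4) and the RP2D definition (4.1.2) do not use it, and the analyses are descriptive. The DLT population requires all scheduled Cycle 1 treatments unless a DLT occurs, so the ratio cannot hide a missed Cycle 1 dose from the escalation decision. Infusion counts and reduced or delayed doses are reported in the same paragraph, and the SAP adds delay summaries and administration listings. All of this stands. A reader might infer that the RP2D could be biased or that missed doses would go unseen; the documents support neither.

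It can also be said that the percentages need a denominator that no document supplies, that a loss present from the first infusion is the extreme case, and that the SAP's weight rule would ignore a 5% change. That is correct, and it limits the figures to illustrations. It does not rescue the rule: without that denominator the Part B ratio has no meaning, and the version in which weight cancels is written nowhere.

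Finally, the SAP predates Part B, so its missing cohorts are version lag, and the protocol defers detail to a separate SAP. That is fair for the tables. But the weight rule is in the current protocol, and a new SAP that followed it would inherit the problem.

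**Conclusion.** The point holds as a wrong rule in the current protocol with a contained effect. The scope rule puts Part B under 12.5.1, Part B doses are fixed, and neither document defines a planned value against which per-kg intensity could be compared. Part B RDI is undefined as written. If planned mg/kg is assumed at baseline weight, it reads about 111% or 91% for full dosing with a sustained 10% loss or gain, and a sustained 10% loss offsets 10% of infusions missed. With gradual loss the error is smaller: 96.6% against 91.7% in the case worked. How often such weight changes would occur cannot be judged from the documents.

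The consequence is a misleading description of Part B exposure within the safety profile. It does not reach dose escalation or the RP2D rule. It should be corrected before the Part B exposure tables are programmed.

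**What to change.** **Protocol 12.5.1.** Limit only the sentences on weight to Part A, and keep the list of exposure outputs for both parts. Labelling the whole paragraph as Part A would remove treatment duration, subjects by cycle and infusion counts from Part B, and these are what reveal missed doses. For Part B, report cumulative dose in mg, dose intensity in mg/week, and RDI as mg given divided by mg planned over the same scheduled weeks. Planned weekly dose is the cohort dose for the a and c cohorts. For 6b, 7b and 8b it is 4/6 of the cohort dose averaged over a full cycle: 66.7, 100 and 133.3 mg/week. Count Part B reductions against protocol Table 12.

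**SAP.** Add the Part B cohorts to Tables 1 and 2. For Part B, remove the 14-day subtraction and the 21-day Cycle 1 observation allowance from the duration formulas. Reconcile the Part A weight rule: protocol 12.5.1 uses the most recent weight, SAP 5.2.1.4 uses baseline unless it has changed by at least 10%.

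**Cost.** Wording in two documents and a Part B exposure derivation. Doses in mg and infusion dates are already collected, and no dose or clinical rule changes.
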